8.7. Hospitalization

Hospitalization is defined as any initial admission (even less than 24 hours) in a hospital or equivalent healthcare facility or any prolongation of an existing admission. Admission also includes transfer within the hospital to an acute/intensive care unit (eg, from the psychiatric

wing to a medical floor, medical floor to a coronary care unit, or neurological floor to a tuberculosis unit). An emergency room visit does not necessarily constitute a hospitalization; however, the event leading to the emergency room visit should be assessed for medical importance.

Hospitalization does not include the following:

- Rehabilitation facilities;
- Hospice facilities;
- Respite care (eg, caregiver relief);
- Skilled nursing facilities;
- Nursing homes;
- Same-day surgeries (as outpatient/same-day/ambulatory procedures).

Hospitalization or prolongation of hospitalization in the absence of a precipitating, clinical AE is not in itself an SAE. Examples include:

- Admission for treatment of a preexisting condition not associated with the development of a new AE or with a worsening of the preexisting condition (eg, for workup of persistent pretreatment laboratory abnormality);
- Social admission (eg, subject has no place to sleep);
- Administrative admission (eg, for yearly physical examination);
- Protocol-specified admission during a study (eg, for a procedure required by the study protocol);
- Optional admission not associated with a precipitating clinical AE (eg, for elective cosmetic surgery);
- Hospitalization for observation without a medical AE;
- Preplanned treatments or surgical procedures. These should be noted in the baseline documentation for the entire protocol and/or for the individual subject;

Diagnostic and therapeutic noninvasive and invasive procedures, such as surgery, should not be reported as AEs. However, the medical condition for which the procedure was performed should be reported if it meets the definition of an AE. For example, an acute appendicitis that begins during the AE reporting period should be reported as the AE and the resulting appendectomy should be recorded as treatment of the AE.

8.8. Severity Assessment

If required on the AE CRFs, the investigator will use the adjectives MILD, MODERATE, or SEVERE to describe the maximum intensity of the AE. For purposes of consistency, these intensity grades are defined as follows:	
MILD	Does not interfere with subject's usual function.
MODERATE	Interferes to some extent with subject's usual function.
SEVERE	Interferes significantly with subject's usual function.

Note the distinction between the severity and the seriousness of an AE. A severe event is not necessarily an SAE. For example, a headache may be severe (interferes significantly with the subject's usual function) but would not be classified as serious unless it met one of the criteria for SAEs, listed above.

8.9. Causality Assessment

The investigator's assessment of causality must be provided for all AEs (serious and non-serious); the investigator must record the causal relationship in the CRF, as appropriate, and report such an assessment in accordance with the SAE reporting requirements if applicable. An investigator's causality assessment is the determination of whether there exists a reasonable possibility that the investigational product caused or contributed to an AE; generally the facts (evidence) or arguments to suggest a causal relationship should be provided. If the investigator does not know whether or not the investigational product caused the event, then the event will be handled as "related to investigational product" for reporting purposes, as defined by the sponsor (see the section on [Reporting Requirements](#)). If the investigator's causality assessment is "unknown but not related to investigational product," this should be clearly documented on study records.

In addition, if the investigator determines that an SAE is associated with study procedures, the investigator must record this causal relationship in the source documents and CRF, as appropriate, and report such an assessment in accordance with the SAE reporting requirements, if applicable.

8.10. Exposure During Pregnancy

For both unapproved/unlicensed products and for marketed products, an exposure during pregnancy occurs if:

1. A female becomes, or is found to be, pregnant either while receiving or having been exposed (eg, because of treatment or environmental exposure) to the investigational product; or the female becomes or is found to be pregnant after discontinuing and/or being exposed to the investigational product;

An example of environmental exposure would be a case involving direct contact with a Pfizer product in a pregnant woman (eg, a nurse reports that she is pregnant and has been exposed to chemotherapeutic products).

2. A male has been exposed (eg, because of treatment or environmental exposure) to the investigational product prior to or around the time of conception and/or is exposed during his partner's pregnancy.

If a study subject or study subject's partner becomes or is found to be pregnant during the study subject's treatment with the investigational product, the investigator must submit this information to the Pfizer drug safety unit on an SAE report form and an EDP supplemental form, regardless of whether an SAE has occurred. In addition, the investigator must submit information regarding environmental exposure to a Pfizer product in a pregnant woman (eg, a subject reports that she is pregnant and has been exposed to a cytotoxic product by inhalation or spillage) using the EDP supplemental form. This must be done irrespective of whether an AE has occurred and within 24 hours of awareness of the exposure. The information submitted should include the anticipated date of delivery (see below for information related to termination of pregnancy).

Follow-up is conducted to obtain general information on the pregnancy and its outcome for all EDP reports with an unknown outcome. The investigator will follow the pregnancy until completion (or until pregnancy termination) and notify Pfizer of the outcome as a follow-up to the initial EDP supplemental form. In the case of a live birth, the structural integrity of the neonate can be assessed at the time of birth. In the event of a termination, the reason(s) for termination should be specified and, if clinically possible, the structural integrity of the terminated fetus should be assessed by gross visual inspection (unless preprocedure test findings are conclusive for a congenital anomaly and the findings are reported).

If the outcome of the pregnancy meets the criteria for an SAE (ie, ectopic pregnancy, spontaneous abortion, intrauterine fetal demise, neonatal death, or congenital anomaly [in a live-born baby, a terminated fetus, an intrauterine fetal demise, or a neonatal death]), the investigator should follow the procedures for reporting SAEs.

Additional information about pregnancy outcomes that are reported as SAEs follows:

- Spontaneous abortion includes miscarriage and missed abortion;
- Neonatal deaths that occur within 1 month of birth should be reported, without regard to causality, as SAEs. In addition, infant deaths after 1 month should be reported as SAEs when the investigator assesses the infant death as related or possibly related to exposure to the investigational product.

Additional information regarding the EDP may be requested by the investigator. Further follow-up of birth outcomes will be handled on a case-by-case basis (eg, follow-up on preterm infants to identify developmental delays). In the case of paternal exposure, the investigator will provide the study subject with the Pregnant Partner Release of Information Form to deliver to his partner. The investigator must document in the source documents that the subject was given the Pregnant Partner Release of Information Form to provide to his partner.

8.11. Occupational Exposure

An occupational exposure occurs when, during the performance of job duties, a person (whether a healthcare professional or otherwise) gets in unplanned direct contact with the product, which may or may not lead to the occurrence of an AE.

An occupational exposure is reported to the drug safety unit within 24 hours of the investigator's awareness, using the SAE report form, regardless of whether there is an associated AE/SAE. Since the information does not pertain to a subject enrolled in the study, the information is not reported on a CRF; however, a copy of the completed SAE report form is maintained in the investigator site file.

8.12. Withdrawal Due to Adverse Events (See Also the Section on [Subject Withdrawal](#))

Withdrawal due to AEs should be distinguished from withdrawal due to other causes, according to the definition of AE noted earlier, and recorded on the appropriate AE CRF page.

When a subject withdraws because of an SAE, the SAE must be reported in accordance with the reporting requirements defined below.

8.13. Eliciting Adverse Event Information

The investigator is to report all directly observed AEs and all AEs spontaneously reported by the study subject. In addition, each study subject will be questioned about AEs.

8.14. Reporting Requirements

Each AE is to be assessed to determine if it meets the criteria for SAEs. If an SAE occurs, expedited reporting will follow local and international regulations, as appropriate.

8.14.1. Serious Adverse Event Reporting Requirements

If an SAE occurs, Pfizer is to be notified within 24 hours of investigator awareness of the event.

In particular, if the SAE is fatal or life-threatening, notification to Pfizer must be made immediately, irrespective of the extent of available AE information. This time frame also applies to additional new information (follow-up) on previously forwarded SAE reports as well as to the initial and follow-up reporting of EDP, exposure via breastfeeding, and occupational exposure cases.

In the rare event that the investigator does not become aware of the occurrence of an SAE immediately (eg, if an outpatient study subject initially seeks treatment elsewhere), the investigator is to report the event within 24 hours after learning of it and document the time of his or her first awareness of the AE.

For all SAEs, the investigator is obligated to pursue and provide information to Pfizer in accordance with the time frames for reporting specified above. In addition, an investigator may be requested by Pfizer to obtain specific additional follow-up information in an expedited fashion. This information collected for SAEs is more detailed than that captured on the AE CRF. In general, this will include a description of the AE in sufficient detail to allow for a complete medical assessment of the case and independent determination of possible causality. Information on other possible causes of the event, such as concomitant medications, vaccines, and/or illnesses, must be provided. In the case of a subject death, a summary of available autopsy findings must be submitted as soon as possible to Pfizer or its designated representative.

8.14.2. Nonserious Adverse Event Reporting Requirements

All AEs will be reported on the AE page(s) of the CRF. It should be noted that the form for collection of SAE information is not the same as the AE CRF. Where the same data are collected, the forms must be completed in a consistent manner. For example, the same AE term should be used on both forms. AEs should be reported using concise medical terminology on the CRFs as well as on the form for collection of SAE information.

8.14.3. Sponsor's Reporting Requirements to Regulatory Authorities

AE reporting, including suspected unexpected serious adverse reactions, will be carried out in accordance with applicable local regulations.

9. DATA ANALYSIS/STATISTICAL METHODS

This section outlines the key planned statistical summaries and analyses for the data collected in this study. A comprehensive overall Statistical Analysis Plan (SAP) will be provided prior to the un-blinding of the trial. The SAP may modify the plans outlined in the protocol; however, any major modifications of planned analyses will be reflected in a protocol amendment if it is modified before data un-blinding. If, after the trial is un-blinded, changes are made to the SAP, then these deviations to the plan will be documented, along with an explanation as to why they occurred, in the Clinical Study Report (CSR).

9.1. Sample Size Determination

The sample size is based on the primary efficacy endpoint, IGA response rate of clear or almost clear and ≥ 2 points improvement at Week 12. For IGA response rate at Week 12, a total of 250 randomized subjects in the 5 treatment groups (providing approximately 200 completers, 40 completers per treatment group assuming 20% dropout rate) will provide approximately 95% power to detect a 33% difference between PF-04965842 and placebo assuming placebo response rate is approximately 10%, and significance level is 0.0125 (Bonferroni adjusted with 4 comparisons).

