The sample size is based on the primary efficacy endpoint, IGA response rate of clear or almost clear and ≥ 2 points improvement at Week 12. For IGA response rate at Week 12, a total of 250 randomized subjects from the 5 treatment groups (providing approximately 200 completers, 40 completers per treatment group assuming 20% dropout rate) will provide approximately 95% power to detect a 33% difference between PF-04965842 and placebo assuming placebo response rate is approximately 10%, and significance level is 0.0125 (Bonferroni adjusted with 4 comparisons).

Efficacy Analysis

Analysis of the Primary Endpoint

When the 12 week treatment period is completed, the analysis of the primary endpoint will be conducted. The primary endpoint is the proportion of IGA responders at Week 12 and the corresponding primary analysis will be based on the normal approximation for the difference in binomial proportions (such as IGA response rates) to test the superiority of each dose of PF-04965842 to placebo at Week 12. Subjects who receive at least one treatment and discontinue from the study before Week 12 will be considered non-responders for the primary endpoint (IGA) for all subsequent visits during the treatment phase until Week 12.

Sensitivity analysis will be performed with a generalized linear mixed model if there are no convergence issues. The modified intention-to-treat (mITT) population will be the subjects who receive at least one dose of randomized investigational product (PF-04965842 or placebo). In addition, dose-response analysis using an E_{\max} model may be provided for the primary endpoint.

Analysis of the Secondary Endpoints

The key secondary endpoint is the percent change from baseline in EASI score at Week 12. The estimates for treatment effect will be obtained by fitting the mixed-effect models repeated measures (MMRM) assuming missing at random if there is no convergence issue to the percent change of EASI score from baseline score. MMRM will also be employed for other continuous secondary endpoints.

In addition to the primary analysis based on the pairwise evaluation of the treatment effects, we will explore the modeling of dose-response relationship for the key secondary endpoint.

The binary secondary endpoints will be analyzed using the same method specified for the primary endpoint.

Analysis of Other Endpoints

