4.2.2. Multiplicity Adjustment

The multiplicity adjustments are considered only in the analysis of the primary endpoint when the Emax model does not fit. Hochberg method (Hochberg, 1988) is used to account for that the null hypothesis will be rejected if a treatment effect is detected at Week 12. The overall Type I family-wise error rate (FWER) is controlled at 0.05 (one-sided).

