4.2.4. Efficacy Analysis and Sample Size Justification

The sample size is based on the primary efficacy endpoint, IGA response rate of clear or almost clear and ≥ 2 points improvement at Week 12. For IGA response rate at Week 12, a total of 250 randomized subjects in the 5 treatment groups (providing approximately 200 completers, 40 completers per treatment group assuming 20% dropout rate) will provide approximately 95% power to detect a 33% difference between PF-04965842 and placebo assuming placebo response rate is approximately 10%, and significance level is 0.0125 (Bonferroni adjusted with 4 comparisons).

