5. ANALYSIS SETS

5.1. Full Analysis Set

As specified in the protocol, the analysis of the efficacy, health outcome and biomarker endpoints will be performed for the modified intent-to-treat (mITT) population, defined as all randomized subjects who receive at least 1 dose of investigational product. This population is also called as the Full Analysis Set (FAS). All subjects from site 1015 (total = 4 subjects) will be excluded from FAS due to major protocol deviations.

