7.1. Efficacy Data

[figure not shown]
For the binary efficacy data such as IGA response, subjects who receive at least one investigational product and discontinue from the study before Week 12 will be considered as non-responders (NR) for all subsequent visits during the treatment phase until Week 12.

For the continuous efficacy endpoints such as percent change from baseline in EASI score at Week 12, the observed case (OC) approach and the last efficacy observation carrying forward (LOCF) missing value imputation will both be considered. The efficacy endpoints will be set to missing after rescue treatment is used. The LOCF method will then be used to impute missing values.

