8.2.2.1. Analysis for the Primary Endpoint

The primary efficacy endpoint is the IGA response at Week 12. The primary analysis data will be based on FAS population with NR as missing value imputation method. Baseline is defined as the score for each assessment prior to the first dosing. .

The objective for the analysis of primary endpoint is to characterize the dose response in inducing clinical IGA reduction in subjects with moderate to severe atopic dermatitis. To achieve this objective, a three parameter Emax dose response model specified in [Section 8.1.1.1](#) will be used as the primary analysis approach to characterize the dose response relationship.

As sensitivity analyses, GLMM will be employed on IGA response from all visits including follow-up. These analyses will be carried out on the FAS population with OC as described in [Section 8.1.1.1](#). P-values and 90% confidence intervals for odds ratios between treatments and placebo will be computed at each visit. Logistic regression will be performed at each visit on FAS with NR as additional sensitivity analysis.

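### Does the stated 95% power fail because the sample-size sentence mentions 40 completers per arm?

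*Protocol*

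**What the plan says.** Protocol 9.1 bases the sample size on IGA response at Week 12. It starts from "a total of 250 randomized subjects in the 5 treatment groups", adds in brackets the expected yield of completers, and states that this number "will provide approximately 95% power to detect a 33% difference between PF-04965842 and placebo assuming placebo response rate is approximately 10" per cent. The significance level is 0.0125, described as Bonferroni for four comparisons. The Protocol Summary has the same sentence ("a total of 250 randomized subjects from the 5 treatment groups (providing approximately 200 completers, 40 completers per treatment group assuming 20% dropout rate"), and SAP 4.2.4 repeats it, again with the bracket "providing approximately 200 completers, 40 completers per treatment group assuming 20% dropout rate".

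Four other places bear on how to read it:

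- SAP 4.2.2 gives the error rate and its direction: "The overall Type I family-wise error rate (FWER) is controlled at 0.05 (one-sided".
- SAP 5.1 sets the efficacy population: "defined as all randomized subjects who receive at least 1 dose of investigational product", less four subjects from one site.
- SAP 7.1 says that dosed subjects who leave before Week 12 "will be considered as non-responders (NR) for all subsequent visits during the treatment phase until Week 12". Protocol 9.2.1 has the same rule.
- SAP 8.2.2.1 says that a three-parameter Emax model "will be used as the primary analysis approach to characterize the dose response relationship". Under SAP 4.2.2, multiplicity-adjusted testing applies only when that model does not fit. Protocol 9.2.1 makes the pairwise comparisons primary.

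**The concern.** The only per-arm number printed in the sample-size sentence is 40. A common convention is to find the evaluable number needed for the target power and then inflate it for dropout, and 40/(1 − 0.20) = 50 fits that pattern exactly. Read so, the 95% should come from 40 per arm, and it does not. The sentence also leaves out whether 0.0125 is one- or two-sided, and whether 10% and 43% already count dropouts as failures.

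If 40 per arm were the true basis, the chance of missing a real 33-point effect at a given dose would be 8.6% to 11.7% one-sided, or 13.4% to 18.1% two-sided, against the 5% implied. Someone interpreting a null result for one dose would then be relying on a sensitivity the trial did not have.

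**Working it through.** **Inputs.** Placebo rate p₀ = 0.10 and difference 0.33, so active rate p₁ = 0.43 (Protocol 9.1, read as an absolute difference). 250 randomized over five equal arms gives 50 per arm; 40 completers per arm at 20% dropout. Level 0.0125. The test is the normal approximation for a difference in proportions (Protocol 9.2.1). The variance form is not stated, so both are shown.

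**Formulas**, with n per arm, d = p₁ − p₀ and p̄ the mean of the two rates:

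- SE_u = √{[p₀(1−p₀) + p₁(1−p₁)]/n}; SE_p = √{2p̄(1−p̄)/n}
- Unpooled power = Φ(d/SE_u − z)
- Pooled power = Φ((d − z·SE_p)/SE_u)
- z = 2.241 for one-sided 0.0125; z = 2.498 for two-sided 0.0125

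**Which inputs the plan itself points to.** SAP 4.2.2 gives 0.05 one-sided for the family; 0.05/4 = 0.0125, so the level in the power sentence is one-sided. SAP 5.1 and 7.1 keep dosed dropouts in the denominator, so n is about 50.

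**The plan's figure, n = 50, one-sided.**

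- SE_u = √[(0.0900 + 0.2451)/50] = 0.0819
- p̄ = 0.265; SE_p = √[2 × 0.265 × 0.735/50] = 0.0883
- Unpooled: 0.33/0.0819 = 4.031; Φ(4.031 − 2.241) = Φ(1.790) = 96.3%
- Pooled: (0.33 − 2.241 × 0.0883)/0.0819 = 1.614; Φ(1.614) = 94.7%

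The arcsine approximation gives 95.5%, and exact enumeration of the pooled z-test gives 95.4%. The stated 95% is reproduced. Spreading the four excluded subjects over the arms (n = 49) gives 96.0% and 94.2%, so that exclusion does not matter.

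**The reading that fails, n = 40.**

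- SE_u = √(0.3351/40) = 0.0915; 0.33/0.0915 = 3.605
- One-sided, unpooled: Φ(3.605 − 2.241) = 91.4%
- Two-sided, unpooled: Φ(3.605 − 2.498) = 86.6%

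**All readings at 0.0125 (unpooled / pooled):**

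| Basis | One-sided | Two-sided |
|---|---|---|
| 50 per arm, 10% vs 43% | 96.3% / 94.7% | 93.7% / 91.0% |
| 40 per arm, 10% vs 43% | 91.4% / 88.3% | 86.6% / 81.9% |
| 50 per arm, 8% vs 34.4% | 87.9% / 85.2% | 82.0% / 78.0% |

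The last row assumes that 10% and 43% are completer rates and that 20% drop out equally from each arm, all counted as failures: 0.80 × 10% = 8% and 0.80 × 43% = 34.4%.

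**The case for a change.** The strongest case for acting is that 95% needs three things to hold together, and the power sentence states none of them plainly: n is 50, not the printed 40; the test is one-sided; and the assumed rates already count dropouts as non-responders. The third is the most serious. The rule that justifies n = 50 also dilutes the rates if they were taken from completers, and power then falls to 85.2%–87.9% one-sided. The quoted power also describes pairwise tests, while the SAP's primary analysis is the Emax model, for which no power is given. Stating all this would cost a sentence or two.

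Much of this stands as description. The sentence is incomplete, and its bracket invites the 40-per-arm reading. But two of the three conditions can be settled from elsewhere in the plan. The 250 randomized are the subject of the power sentence and match the planned denominator, and sidedness is in SAP 4.2.2. On the third, the rates are given for the primary endpoint, which Protocol 9.2.1 analyses with dropouts as non-responders, so the natural reading is that they are on that definition. The completer-rate reading is possible, but nothing in the documents supports it. The failing reading, in contrast, needs a completers-only denominator that neither Protocol 9.2.1 nor SAP 8.1.1.1 uses for the primary endpoint.

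The pairwise-versus-Emax difference is a separate matter between the two documents and says nothing about whether 95% was computed correctly. The SAP's fallback is Hochberg, which rejects whatever Bonferroni rejects, so for a given n, sidedness and pair of rates the Bonferroni figures do not overstate its power.

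**Conclusion.** The concern does not hold as an error in the power figure. About 95% follows from the plan's own inputs: 50 dosed subjects per arm, dropouts as non-responders, 10% versus 43%, and one-sided 0.0125 (94.7% pooled, 96.3% unpooled). Even two-sided, the unpooled figure at 50 per arm is 93.7%, though pooled it is 91.0%. The shortfall to 88%–91% one-sided appears only with 40 per arm, which is not the analysed number.

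This rests on two readings: that the sidedness in SAP 4.2.2 applies to the power sentence, and that the assumed rates are on the non-responder definition. The first is well supported by the arithmetic 0.05/4. The second is the natural reading but is not written down.

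What remains is an explanatory gap that a statistician can fill from SAP 4.2.2, 5.1 and 7.1. Filling it would alter neither the number randomized nor any analysis, estimate, confidence interval or error rate. No change follows.
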